Appendix 8 Symbol Digit Modalities Test

The SDMT [Smith 1982, Benedict 2006] measures attention and processing speed much like the PASAT. The SDMT includes a reference key of 9 symbols, each paired with a single digit. Below the reference key are rows of the symbols arranged randomly. The subject is given 90 seconds to say the number that corresponds with each symbol. The test administrator records the answers and the number of correct answers is recorded as the score.

The SDMT will be performed after the MSFC. Study personnel will be trained to administer and score the SDMT. A sample of the SDMT is provided below. Subjects will complete the test on a validated paper form that will be collected and transcribed in the eCRF.

‡	§	¤	¬		₩	Γ	☰	∫						
1	2	3	4	5	6	7	8	9						
∫	¤	¬	∫	‡	§	¬	₩	∫	§	∫	¬			
₩	§	∫	¬	¤	§	‡	₩	∫	¬	§	☰	₩	‡	Γ
₩	¤		Γ	∫	‡		₩	Γ	¤	¬	☰	‡	₩	
¬	₩	¤	∫	§	₩	∫	¤	§		☰	Γ	‡	§	₩
☰	¤	Γ	‡	§		₩	¤	¬	‡		☰	¬	Γ	∫
§	☰		¬	‡	§	₩	☰	☰	∫		¬	¤	§	Γ
¬	Γ		☰	‡		Γ	¤	∫	☰	¬	∫	₩	‡	§

Appendix 9 Fatigue Symptoms and Impacts Questionnaire – Relapsing Multiple Sclerosis

INSTRUCTIONS

This questionnaire asks about your experience with your Relapsing Multiple Sclerosis (relapsing MS).

- This section of the questionnaire asks about your **fatigue-related symptoms** of relapsing MS over the **past 24 hours**.

Please select the response that best describes your experience. Please answer all of the questions and do not skip any. There are no right or wrong answers to any of the questions.

[figure not shown]
Section 1

Please enter today's date: DD/MM/YYYY

[figure not shown]
Instructions:

Please select the response that best describes your experience with **relapsing MS symptoms** in the **past 24 hours** while doing routine daily activities (e.g. housework, yard work, shopping, working).

[figure not shown]
1. In the past 24 hours, while doing routine daily activities, how physically tired did you feel?

[figure not shown]
2. In the past 24 hours, while doing routine daily activities, how mentally tired did you feel?

[figure not shown]
3. In the past 24 hours, while doing routine daily activities, how physically weak did you feel?

[figure not shown]
4. In the past 24 hours, how would you rate your energy while doing routine daily activities?

5. In the past 24 hours, while doing routine daily activities, how worn out did you feel?

[figure not shown]
6. In the past 24 hours, while doing routine daily activities, how sleepy did you feel?

Instructions:

Please select the response that best describes your experience with **relapsing MS symptoms** in the **past 24 hours while at rest** (e.g. reading a book, watching TV).

7. In the past 24 hours, how worn out did you feel while at rest?

Section 2

INSTRUCTIONS

This questionnaire asks about your experience with your Relapsing Multiple Sclerosis (relapsing MS).

This section of the questionnaire asks about **how your life was affected** by fatigue-related symptoms of relapsing MS in the **past 7 days**.

Please select the response that best describes your experience. Please answer all of the questions and do not skip any. There are no right or wrong answers to any of the questions.

Instructions:

Please read and answer each of the following questions by selecting the response that best describes your **experience** in the **past 7 days**.

1. Thinking about your **fatigue-related symptoms** over the past 7 days, how much difficulty did you have running errands (such as grocery shopping or going to the bank or ATM)?
 ₀ No difficulty
 ₁ A little difficulty
 ₂ Moderate difficulty
 ₃ Quite a bit of difficulty
 ₄ Extreme difficulty

2. Thinking about your **fatigue-related symptoms** over the past 7 days, how much difficulty did you have communicating clearly?
 ₀ No difficulty
 ₁ A little difficulty
 ₂ Moderate difficulty
 ₃ Quite a bit of difficulty
 ₄ Extreme difficulty

3. Thinking about your **fatigue-related symptoms** over the past 7 days, how much difficulty did you have thinking clearly?

0 No difficulty
1 A little difficulty
2 Moderate difficulty
3 Quite a bit of difficulty
4 Extreme difficulty

4. Thinking about your **fatigue-related symptoms** over the past 7 days, how difficult was it for you to motivate yourself to do routine daily activities?

0 Not difficult
1 A little difficult
2 Moderately difficult
3 Quite difficult
4 Extremely difficult

5. Thinking about your **fatigue-related symptoms** over the past 7 days, how much difficulty did you have doing indoor household chores?

0 No difficulty
1 A little difficulty
2 Moderate difficulty
3 Quite a bit of difficulty
4 Extreme difficulty

6. Thinking about your **fatigue-related symptoms** over the past 7 days, how much difficulty did you have walking?

₀ No difficulty
 ₁ A little difficulty
 ₂ Moderate difficulty
 ₃ Quite a bit of difficulty
 ₄ Extreme difficulty

7. Thinking about your **fatigue-related symptoms** over the past 7 days, how much difficulty did you have maintaining relationships with people you are close to?

₀ No difficulty
 ₁ A little difficulty
 ₂ Moderate difficulty
 ₃ Quite a bit of difficulty
 ₄ Extreme difficulty

8. Thinking about your **fatigue-related symptoms** over the past 7 days, how much difficulty did you have taking part in social activities (such as going to the movies or going out to eat)?

₀ No difficulty
 ₁ A little difficulty
 ₂ Moderate difficulty
 ₃ Quite a bit of difficulty
 ₄ Extreme difficulty

9. Thinking about your **fatigue-related symptoms** over the past 7 days, how frustrated were you?

0 Not at all
1 A little bit
2 Somewhat
3 Quite a bit
4 Extremely

10. Thinking about your **fatigue-related symptoms** over the past 7 days, how often were you forgetful?

0 Never
1 Rarely
2 Some of the time
3 Most of the time
4 Almost all of the time

11. Thinking about your **fatigue-related symptoms** over the past 7 days, how often did you have to take a nap?

0 Never
1 Rarely
2 Some of the time
3 Most of the time
4 Almost all of the time

12. Thinking about your **fatigue-related symptoms** over the past 7 days, how often did you have to take a break?

0 Never
1 Rarely
2 Some of the time
3 Most of the time
4 Almost all of the time

13. Thinking about your **fatigue-related symptoms** over the past 7 days, how often did you have to rearrange your plans?

0 Never
1 Rarely
2 Some of the time
3 Most of the time
4 Almost all of the time

Appendix 10 SF-36v2™

SF-36v2® Health Survey © 1992, 2000, 2009
Medical Outcomes Trust and
QualityMetric Incorporated.

All rights reserved.

SF-36® is a registered trademark of
Medical Outcomes Trust.
(SF-36v2® Health Survey Standard,
United States (English))

Your Health and Well-Being

This survey asks for your views about your health. This information will help keep track of how you feel and how well you are able to do your usual activities. Thank you for completing this survey!

For each of the following questions, please select the one response that best describes your answer.

In general, would you say your health is:

Excellent
Very good
Good
Fair
Poor

Compared to one year ago, how would you rate your health in general now?

Much better now than one year ago
Somewhat better now than one year ago
About the same as one year ago
Somewhat worse now than one year ago
Much worse now than one year ago

The following questions are about activities you might do during a typical day.

Does your health now limit you in these activities? If so, how much?

Does your health now limit you in vigorous activities, such as running, lifting heavy objects, participating in strenuous sports? If so, how much?

- Yes, limited a lot
- Yes, limited a little
- No, not limited at all

Does your health now limit you in moderate activities, such as moving a table, pushing a vacuum cleaner, bowling, or playing golf? If so, how much?

- Yes, limited a lot
- Yes, limited a little
- No, not limited at all

Does your health now limit you in lifting or carrying groceries? If so, how much?

- Yes, limited a lot
- Yes, limited a little
- No, not limited at all

Does your health now limit you in climbing several flights of stairs? If so, how much?

- Yes, limited a lot
- Yes, limited a little
- No, not limited at all

Does your health now limit you in climbing one flight of stairs? If so, how much?

Yes, limited a lot
Yes, limited a little
No, not limited at all

Does your health now limit you in bending, kneeling, or stooping? If so, how much?

Yes, limited a lot
Yes, limited a little
No, not limited at all

Does your health now limit you in walking more than a mile? If so, how much?

Yes, limited a lot
Yes, limited a little
No, not limited at all

Does your health now limit you in walking several hundred yards? If so, how much?

Yes, limited a lot
Yes, limited a little
No, not limited at all

Does your health now limit you in walking one hundred yards? If so, how much?

Yes, limited a lot
Yes, limited a little
No, not limited at all

Does your health now limit you in bathing or dressing yourself? If so, how much?

Yes, limited a lot
Yes, limited a little
No, not limited at all

During the past 4 weeks, how much of the time have you had any of the following problems with your work or other regular daily activities as a result of your physical health?

During the past 4 weeks, how much of the time have you cut down on the amount of time you spent on work or other activities as a result of your physical health?

- All of the time
- Most of the time
- Some of the time
- A little of the time
- None of the time

During the past 4 weeks, how much of the time have you accomplished less than you would like as a result of your physical health?

- All of the time
- Most of the time
- Some of the time
- A little of the time
- None of the time

During the past 4 weeks, how much of the time were you limited in the kind of work or other activities as a result of your physical health?

- All of the time
- Most of the time
- Some of the time
- A little of the time
- None of the time

During the past 4 weeks, how much of the time have you had difficulty

performing the work or other activities as a result of your physical health (for example, it took extra effort)?

All of the time
Most of the time
Some of the time
A little of the time
None of the time

During the past 4 weeks, how much of the time have you had any of the following problems with your work or other regular daily activities as a result of any emotional problems (such as feeling depressed or anxious)?

During the past 4 weeks, how much of the time have you cut down on the amount of time you spent on work or other activities as a result of any emotional problems (such as feeling depressed or anxious)?

All of the time
Most of the time
Some of the time
A little of the time
None of the time

During the past 4 weeks, how much of the time have you accomplished less than you would like as a result of any emotional problems (such as feeling depressed or anxious)?

All of the time
Most of the time
Some of the time
A little of the time
None of the time

During the past 4 weeks, how much of the time have you done work or other activities less carefully than usual as a result of any emotional problems (such as feeling depressed or anxious)?

All of the time
Most of the time
Some of the time
A little of the time
None of the time

During the past 4 weeks, to what extent has your physical health or emotional problems interfered with your normal social activities with family, friends, neighbors, or groups?

Not at all
Slightly
Moderately
Quite a bit
Extremely

How much bodily pain have you had during the past 4 weeks?

None
Very mild
Mild
Moderate
Severe
Very severe

During the past 4 weeks, how much did pain interfere with your normal work (including both work outside the home and housework)?

Not at all
A little bit
Moderately
Quite a bit
Extremely

These questions are about how you feel and how things have been with you during the past 4 weeks. For each question, please give the one answer that

comes closest to the way you have been feeling.

How much of the time during the past 4 weeks did you feel full of life?

All of the time
Most of the time
Some of the time
A little of the time
None of the time

How much of the time during the past 4 weeks have you been very nervous?

All of the time
Most of the time
Some of the time
A little of the time
None of the time

How much of the time during the past 4 weeks have you felt so down in the dumps that nothing could cheer you up?

All of the time
Most of the time
Some of the time
A little of the time
None of the time

How much of the time during the past 4 weeks have you felt calm and peaceful?

All of the time
Most of the time
Some of the time
A little of the time
None of the time

How much of the time during the past 4 weeks did you have a lot of energy?

All of the time
Most of the time
Some of the time
A little of the time
None of the time

How much of the time during the past 4 weeks have you felt downhearted and depressed?

All of the time
Most of the time
Some of the time
A little of the time
None of the time

How much of the time during the past 4 weeks did you feel worn out?

All of the time
Most of the time
Some of the time
A little of the time
None of the time

How much of the time during the past 4 weeks have you been happy?

All of the time
Most of the time
Some of the time
A little of the time
None of the time

How much of the time during the past 4 weeks did you feel tired?

All of the time

Most of the time
Some of the time
A little of the time
None of the time

During the past 4 weeks, how much of the time has your physical health or emotional problems interfered with your social activities (like visiting with friends, relatives, etc.)?

All of the time
Most of the time
Some of the time
A little of the time
None of the time

How TRUE or FALSE is each of the following statements for you?

I seem to get sick a little easier than other people.

Definitely true
Mostly true
Don't know
Mostly false
Definitely false

I am as healthy as anybody I know.

Definitely true
Mostly true
Don't know
Mostly false
Definitely false

I expect my health to get worse.

Definitely true

Mostly true
Don't know
Mostly false
Definitely false

My health is excellent.

Definitely true
Mostly true
Don't know
Mostly false
Definitely false

Appendix 11 Work Productivity and Activity Impairment Questionnaire: Multiple Sclerosis

Work Productivity and Activity Impairment Questionnaire: Multiple Sclerosis V2.0 (WPAI:MS)

The following questions ask about the effect of your multiple sclerosis on your ability to work and perform normal daily activities. *Please fill in the blanks or circle a number, as indicated.*

1. Are you currently employed (working for pay)? NO YES
If NO, tick "NO" and skip to question 6.

The next questions refer to the **past seven days**, not including today.

2. During the past seven days, how many hours did you miss from work because of problems associated with your multiple sclerosis? *Include hours you missed on sick days, times you went in late, left early, etc., because of your multiple sclerosis. Do not include time you missed to participate in this study.*

HOURS

3. During the past seven days, how many hours did you miss from work because of any other reason, such as annual leave, holidays, time off to participate in this study?

HOURS

[figure not shown]
4. During the past seven days, how many hours did you actually work?

HOURS *(If "0", skip to question 6)*

5. During the past seven days, how much did your multiple sclerosis affect your productivity while you were working?

Think about days you were limited in the amount or kind of work you could do, days you accomplished less than you would like, or days you could not do your work as carefully as usual. If multiple sclerosis affected your work only a little, choose a low number. Choose a high number if multiple sclerosis affected your work a great deal.

[figure not shown]
Consider only how much multiple sclerosis affected productivity while you were working.

6. During the past seven days, how much did your multiple sclerosis affect your ability to perform your normal daily activities, other than work at a job?

By normal activities, we mean the usual activities you perform, such as working around the house, shopping, childcare, exercising, studying, etc. Think about times you were limited in the amount or kind of activities you could perform and times you accomplished less than you would like. If multiple sclerosis affected your activities only a little, choose a low number. Choose a high number if multiple sclerosis affected your activities a great deal.

Consider only how much multiple sclerosis affected your ability to do your normal daily activities, other than work at a job.

Appendix 12 Relapse assessment questionnaire

TO BE FILLED OUT BY THE TREATING NEUROLOGIST AND/OR STUDY NURSE

When applicable, for each of the Questions 1 to 5 below, complete either the phone interview or visit interview questions.

Phone interview 	Visit interview During a visit at the study site (scheduled or unscheduled)
 Subject calling the site to report new/worsened symptoms  Scheduled call from the site to the subject for relapse detection	
Date of phone interview dd mmm yy	Date of visit dd mmm yy

1. Is / was the subject having new neurological symptom(s) or an acute worsening of pre-existing neurological symptom(s)?

	Visit
 Yes → Go to Question 2  No → STOP Relapse investigation	 Yes → Go to Question 2  No → STOP Relapse investigation

2. Are / were symptoms suggestive of a relapse (e.g. rapid onset, typically hours or days as opposed to weeks/months, symptom type)?

	Visit
 Yes/possibly → Go to Question 3  Definitely not → STOP Relapse investigation and enter subject's symptoms or diagnosis on the eCRF AE page	 Yes/possibly → Go to Question 3  Definitely not → STOP Relapse investigation and enter subject's symptoms or diagnosis on the AE eCRF page

3. Did the symptoms last > 24 hours?

	Visit
---	--------------

 Yes/possibly → Go to Question 5 and complete date and time of start of symptoms
 
 No → Go to Question 4 and complete date and time of start of symptoms
	
 Yes/possibly → Go to Question 5 and complete date and time of start of symptoms
 
 No → Go to Question 4 and complete date and time of start of symptoms

Date of start of symptoms
 
— — — — dd mmm yy
	
Date of start of symptoms
 
— — — — dd mmm yy

Time of start of symptoms
 
— — — — hh mm
	
Time of start of symptoms
 
— — — — hh mm

4. Have the symptoms started within the last 24 hours?

(To be answered only if answer to question 3 was "No")

	Visit

 Yes → Go to Question 5
 
 No → STOP Relapse investigation and enter subject's symptoms or diagnosis on the AE eCRF page
	
 Yes → Go to Question 5
 
 No → STOP Relapse investigation and enter subject's symptoms or diagnosis on the AE eCRF page

5. Does / did the subject have concomitant fever or an infection and, if yes, are/were the symptoms more likely due to fever/infection than to a relapse?

	Visit

 Yes → STOP Relapse investigation and enter subject's symptoms or diagnosis on the AE eCRF page
	
 Yes → STOP Relapse investigation and enter subject's symptoms or diagnosis on the AE eCRF page

- No / not sure → *Invite the subject to an unscheduled relapse assessment visit as soon as possible but at least 24 hours after the onset of symptom(s).*
→ Go to Question 7 but if answer to question 4 was "Yes", answer additionally question 6 at the visit performed at least 24 hours after symptom onset

- No / not sure → *If this visit occurs < 24 hours from symptom onset, invite the subject to an unscheduled relapse assessment visit as soon as possible but at least 24 hours after the onset of symptom(s)*
→ Go to Question 7, but if answer to question 4 was "Yes", answer additionally question 6 at the visit performed at least 24 hours after symptom onset

Question 6 - 8 can only be asked during a visit at the study site (scheduled or unscheduled) which occurs at least 24 hours after the symptoms onset.

Visit interview
during a visit at the study site (scheduled or unscheduled)

Date of visit

(complete only if different from the one reported for question 1 to 5)

— — . — — — . — —
dd mmm yy

6. Did the symptoms last > 24 hours?

(To be answered only at a visit performed at least 24 hours after onset of symptoms and if answer to question 4 was "Yes" during an earlier interview (i.e. an interview conducted within 24 hours from symptom onset):

- Yes / possibly → Go to Question 7
- Definitely not → STOP Relapse investigation and enter subject's symptoms or diagnosis on the AE eCRF page

7. Prior to the onset of this event, were the MS symptom(s) stable or improving over the last 30 days?

- Yes / possibly → Go to Question 8
- No → Choose one option below
 - The previous symptoms corresponded to a relapse, which is recorded in the eCRF

→ STOP the relapse investigation for the new episode and enter the symptoms on the AE eCRF page unless the current symptoms are considered as part of the most recent relapse. Note: New or recurrent symptoms that occur less than 30 days following onset of a protocol-defined relapse should be considered part of the same relapse.

- The previous symptoms were not due to a relapse
 - Go to Question 8 and make sure that those previous symptoms are recorded on the AE eCRF page

8. Is there other and better explanation for the patient's current symptoms than an MS relapse?

- Yes → STOP Relapse investigation and enter patient's symptoms or diagnosis on the AE page
- No → Enter symptoms in the "Relapse symptom form ".
→ The subject should undergo EDSS assessment by the efficacy assessor within 7 days from the relapse onset (Note: no referral is needed at scheduled visits where EDSS/FS score is assessed as part of the scheduled assessment for this visit - in this event, the EDSS assessment planned for this visit will be used as part of the relapse assessment)

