6.1.1 Primary efficacy endpoint

The primary endpoint is ARR. This endpoint is defined as the number of confirmed relapses from randomization up to EOS, per subject-year.

Definition of relapse

- A relapse is defined as new, worsening or recurrent neurological symptoms that occur at least 30 days after the onset of a preceding relapse, and that last at least 24 hours, in the absence of fever or infection.
- The new, worsening or recurrent neurological symptoms are to be evaluated by the treating neurologist and, if all the elements of the above definition have been verified, in the absence of another, better explanation of the subject's symptoms, the event is considered as a relapse [see Section 7.2.2]. The onset date of the relapse corresponds to the onset date of the symptoms.
- A relapse will be confirmed only when the subjects' symptoms are accompanied by an increase in EDSS/FS scores, which is consistent with the subject's symptoms, from a previous clinically stable EDSS/FS assessment (i.e., performed at least 30 days after the onset of any previous relapse), obtained by the efficacy assessor and consistent with the following:
 - an increase of at least half a step (0.5 point; unless EDSS = 0, then an increase of at least 1.0 point is required), or
 - an increase of at least 1.0 point in at least two FS scores, or
 - an increase of at least 2.0 points in at least one FS score (excluding bladder/bowel and cerebral).

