7.2.2 Detection and evaluation of relapses

Detection and evaluation of relapses will be done as follows [see Figure 3]:

Step 1: At every study visit, subjects are reminded to contact their principal investigator / treating neurologist immediately in the event of the appearance of any new or worsening neurological symptoms. In addition, the site will contact the subject in-between the 12-weekly visits (e.g., Visit 6 – Week 12, Visit 7 – Week 24, ...) even after possible premature discontinuation from the study treatment (e.g., Visit 6A – Week 12 in the PTOP, Visit 7A – Week 24 in the PTOP, ...) in order to proactively inquire about any new or worsened neurological symptoms. These telephone calls will be conducted either at Weeks 18, 30, 42, 54, 66, 78, 90, 102, 114, 126, 138 and 150 (\pm 7 days), or 6 weeks after the last 12-weekly visit (\pm 7 days).

Whenever between visits a subject experiences any new or worsening neurological symptoms he/she must contact the principal investigator / treating neurologist, study nurse or clinical coordinator as soon as possible in order to complete a telephone questionnaire for relapse assessment [see [Appendix 12](#)].

If, during the call from the site inquiring about symptoms suggestive of potential new relapses, the subject reports occurrence of such symptoms, a telephone questionnaire for relapse assessment will also be completed.

If a relapse is suspected, the subject will be required to come to the site for an unscheduled relapse assessment visit. The completed telephone questionnaire will be collected in the eCRF.

Step 2: At every scheduled and unscheduled visit (limited to unscheduled visits when the subject will meet with the principal investigator / treating neurologist, but not at other unscheduled visits conducted for repeat testing (e.g., spirometry, liver enzymes), the principal investigator / treating neurologist will interview and examine the subject to determine whether or not a relapse may have occurred since last visit using a dedicated relapse assessment questionnaire [see [Appendix 12](#)] and the relapse symptom form [see [Appendix 13](#)].

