Appendix 13 Relapse symptom form

TO BE FILLED OUT BY THE TREATING NEUROLOGIST

Relapse symptom Form		
Visual (optic) functions		
Did the patient report any new or worsening symptoms belonging to the visual functions?	 Yes	 No
If yes, complete the below		
 Decreased vision		
 Changed vision (excl. double vision) e.g. blurred vision		
 Decreased visual field		
 Scotoma		
 Ocular pain		
 Other If other, please specify:		
Brainstem functions		
Did the patient report any new or worsening symptoms belonging to the brain stem functions?	 Yes	 No
If yes, complete the below		
 Double vision		
 Sudden hearing decrease or loss		
 Oscillopsia		
 Numbness in the face		
 Symptoms of facial nerve weakness (e.g. problems with eye or mouth closure, facial asymmetry)		
 Dysarthria		
 Dysphagia		
 Vertigo		
 Other If other, please specify:		
Pyramidal functions		

Did the patient report any new or worsening symptoms belonging to the pyramidal functions?	 Yes If yes, complete the below	 No
 Weakness in any extremity		
 Muscle stiffness/spasticity		
 Impaired walking or hopping		
 Other		
If other, please specify:		
Cerebellar functions		
Did the patient report any new or worsening symptoms belonging to the cerebellar functions?	 Yes If yes, complete the below	 No
 Difficulties keeping balance while sitting, standing or walking		
 Tremor		
 Vertigo		
 Clumsy movements		
 Other		
If other, please specify:		
Sensory functions		
Did the patient report any new or worsening symptoms belonging to the sensory functions?	 Yes If yes, complete the below	 No
 Any abnormal sensation		
 Tingling		

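### Question 1 of the relapse questionnaire leaves out recurrent symptoms, which the primary endpoint definition counts, so a relapse in which a resolved deficit returns can be stopped at the first step.

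*Protocol*

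**What the plan says.** Section 6.1.1 opens its definition with "A relapse is defined as new, worsening or recurrent neurological symptoms". The next bullet repeats the three categories as the neurologist's task: "The new, worsening or recurrent neurological symptoms are to be evaluated by the treating neurologist".

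Appendix 12, completed by the treating neurologist and/or the study nurse, starts with Question 1: "Is / was the subject having new neurological symptom(s) or an acute worsening of pre-existing neurological symptom(s". The only answers are Yes and No. On both the telephone and the visit branch, No leads to "STOP Relapse investigation".

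The same appendix, in the note to Question 7, says "New or recurrent symptoms that occur less than 30 days following onset of a protocol-defined relapse should be considered part of the same relapse".

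Section 7.2.2 makes this questionnaire the tool for calls and visits. Scheduled calls are there to "proactively inquire about any new or worsened neurological symptoms". Step 2 has the neurologist verify all elements of the Section 6.1.1 definition, and Step 3 places the EDSS/FS assessment within 7 days of symptom onset.

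**The concern.** The case-finding form is narrower than the endpoint it serves. A returning deficit, for example optic neuritis in an eye that had recovered from an earlier episode, is not strictly new to the subject, and it is not a worsening of a symptom that was present. Section 6.1.1 and the Question 7 note both list recurrent separately from new, so the protocol's own usage does not support reading new as including recurrence.

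Confirmed relapses determine the primary endpoint (ARR) and the second secondary endpoint (time to first confirmed relapse). If the form is applied as written, events that the definition counts can end at the first question. Whether they count would then depend on how each of about 100 sites reads that question.

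**Working it through.** **1. The wording side by side**

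| Place | New | Worsening | Recurrent |
|---|---|---|---|
| Section 6.1.1, definition and evaluation bullet | yes | yes | yes |
| Appendix 12, Question 1 | yes | yes (acute) | no |
| Appendix 12, Question 7 note | yes | no | yes |
| Section 7.2.2 calls and reminders; Sections 8.2.5 and 8.4.1; footnotes of Tables 1 to 3 | yes | yes | no |
| Section 11.3.2.2.2, symptom-selection analysis | yes | yes | no |

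**2. What happens after a No at Question 1**

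- *By telephone.* Under Step 1 of Section 7.2.2 the subject is called in only if a relapse is suspected. The comparison with Section 6.1.1 comes in Step 2, at a visit, so a telephone No precedes it.
- *No margin for doubt.* Questions 2, 3, 6 and 7 accept a possible yes and Question 5 accepts uncertainty. Question 1 does not.
- *Timing.* Scheduled calls fall 6 weeks after a 12-weekly visit, so the next scheduled visit is about 12 − 6 = 6 weeks away. That is well past the 7 days of Step 3, and the deficit may have improved by then.
- *What is stored.* The completed form goes into the eCRF. Onset date is first asked at Question 3, and symptoms are entered only after Question 8. A form stopped at Question 1 therefore holds neither. The stops at Questions 2, 4, 5, 6 and 8 direct the symptoms to the AE page; the stop at Question 1 does not.
- *Detection.* The sensitivity analysis in Section 11.3.2.2.2 compares the share of new or worsening symptoms that become relapses. Its base has the same omission.

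**3. Illustrative size**

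Inputs from Sections 11.5.1 and 11.3.2.1: n = 300 per arm, ARR 0.50 and 0.325, k = 1.3, mean follow-up t = 1.9 years, two-sided alpha 0.05.

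Formula: SE² = [1/(t·m0) + 1/(t·m1) + 2k]/n; power = Φ(|ln(m1/m0)|/SE − 1.96).

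The plan's own figure first:

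- 1/(1.9 × 0.50) = 1.0526 and 1/(1.9 × 0.325) = 1.6194
- SE² = (1.0526 + 1.6194 + 2.6)/300 = 0.01757, so SE = 0.1326
- |ln 0.65| = 0.4308, and 0.4308/0.1326 = 3.25
- power = Φ(3.25 − 1.96) = Φ(1.29) = 90.1%, against the stated 90% or so

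The formula also reproduces all nine rows of the table in Section 11.5.3 to within 0.1 point.

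The protocol does not give the share of relapses that are recurrences. Assume a fraction L of all relapses is lost equally in both arms, so both rates are multiplied by 1 − L:

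| L (assumed) | Placebo ARR | Ponesimod ARR | Rate ratio | Power |
|---|---|---|---|---|
| 0 | 0.500 | 0.325 | 0.65 | 90.1% |
| 5% | 0.475 | 0.309 | 0.65 | 89.4% |
| 10% | 0.450 | 0.293 | 0.65 | 88.5% |
| 20% | 0.400 | 0.260 | 0.65 | 86.5% |

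The last row equals the protocol's own entry for 0.400/0.260. The true L would be the share of relapses that are purely recurrent multiplied by the probability that such an event is stopped at Question 1 and not picked up later. If 5% to 20% is taken as the recurrent share, the table treats that probability as 1 and is therefore an upper bound.

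**The case against.** The strongest reply is that the protocol uses new or worsening as shorthand for all relapse symptoms. Step 3 of Section 7.2.2, Section 8.4.1 and Section 11.3.2.2.2 all do so, and a literal reading would exclude recurrences from the whole procedure, against Section 6.1.1. The missing AE instruction at Question 1 also suggests that No was meant for a subject with no neurological event at all. Many interviewers would tick Yes for a deficit that has come back. This stands as a reason why loss is possible but not certain. It does not remove the mismatch, because the form does not define new to include recurrence and its own Question 7 note keeps the two apart.

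The second reply is that other text protects these events:

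- Subjects are also told to report any symptoms suggesting an exacerbation, and Section 8.4.1 requires an interview on that trigger.
- At every scheduled visit the neurologist asks about relapses since the last visit, examines the subject and applies Section 6.1.1.

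This stands, in part. The visit interview uses the same questionnaire, and after a telephone stop it can come too late for a timely EDSS.

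A reader might infer that a stop at Question 1 leaves no record. The documents do not support that: completed questionnaires are collected in the eCRF, the outcome is captured as no relapse, unconfirmed or confirmed, and Section 10.1.1 covers unfavourable symptoms as AEs whatever the form says. What the stopped form lacks is the onset date and the symptoms.

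A reader might also infer that the Appendix 13 prompts drop events. They do not. That form is filled in only after Question 8 and has an open item for other symptoms attributable to a relapse.

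**Conclusion.** The mismatch is real and sits at the entry to the primary endpoint. Applied literally, and above all by telephone, Question 1 can stop a relapse that Section 6.1.1 counts before that definition is consulted. The existing safeguards reduce this risk but do not remove it.

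The size cannot be established from the protocol. On the assumption of 5% to 20% of relapses lost equally in both arms, both ARRs fall in proportion and power drops by about 0.8 to 3.7 points (90.14 − 89.38 and 90.14 − 86.47), while the rate ratio stays at 0.65. It would be tempting to conclude that the treatment effect is biased. Nothing in the document points to a loss that differs by arm, and the trial is double-blind. The supported conclusion is narrower: ascertainment may vary between sites and ARR may be understated. This is worth correcting because it is cheap, and it does not by itself threaten the primary comparison.

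**What to change.** - **Appendix 12, Question 1:** insert *or recurrent* after *new*, so that the question covers new or recurrent symptoms as well as acute worsening of existing ones.
- **Calls and reminders:** use *new, worsening or recurrent* in Sections 7.2.2, 8.2.5 and 8.4.1 and in the relapse footnotes of Tables 1 to 3.
- **Section 11.3.2.2.2:** define the base of the symptom-selection analysis in the same three terms, so that it can show how recurrent symptoms were handled.
- **Appendix 13:** the prompts may be aligned for consistency, but no events depend on it.

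The cost is a few words on the eCRF form, in the call script and in the protocol text. No visit, assessor or change to the primary analysis is needed.
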